5.2.2 Exclusion Criteria – Expansion

1. CCI

[figure not shown]
- 2. Primary CNS tumor or known CNS involvement.
- 3. Has been exposed to any of the following prior therapies within the specified timeframes:
 - Received prior investigational CD30-targeting therapy, CCI
 BV).
 - b. Autologous HSCT within 60 days (applies to both cHL and TCL). Allogeneic HSCT within 90 days (applies to cHL) prior to the first dose of GEN3017.
 - c. Chemotherapy within 2 weeks or major surgery within 4 weeks of the first dose of GEN3017.
 - d. Curative radiotherapy within 4 weeks or palliative radiotherapy within 2 weeks prior to the first dose of GEN3017.
 - e. Treatment with an investigational drug within 4 weeks or 5 half-lives of the drug, whichever is shorter, prior to the first dose of GEN3017 or currently receiving any other investigational agents.
 - f. Prior treatment with live, attenuated vaccines within 30 days prior to the first dose of GEN3017. Examples of live vaccines include, but are not limited to, the following:

Confidential Page 62 of 162

Version: 3.0

measles, mumps, rubella, varicella/zoster (chicken pox), yellow fever, rabies, Bacillus Calmette–Guérin, and typhoid vaccine. Seasonal influenza vaccines for injection are generally killed virus vaccines and are allowed; however, intranasal influenza vaccines (eg, FluMist®) are live attenuated vaccines and are not allowed. Experimental and/or nonauthorized SARS-CoV-2 vaccinations are not allowed.

g. Receiving immunosuppressive drugs or systemic corticosteroids such as prednisone at doses >25 mg daily or its equivalent within 14 days prior to the first dose of GEN3017.

- 7. Active GVHD requiring immune suppression regardless of grade.
- 8. Active infection requiring antibiotic/antifungal/antiviral treatment.
- 9. Active infection with HTLV-1 or HTLV-2
- 10. Has a known history of seropositivity for HIV. Note: HIV testing is required at screening only if required per local health authorities or institutional standards.
- 11. Has known history/positive serology for hepatitis B (unless immune due to vaccination or unless passive immunization due to Ig therapy):
 - a. Positive test for antibodies to anti-HBc

AND

- b. Negative test for antibodies to anti-HBs
- 12. Known medical history or ongoing hepatitis C infection that has not been cured.

13. **CC**

Confidential Page 63 of 162

Document Name: GCT3017-01 - Protocol - 18 Oct 2023 Genmab

Document Number: TMF-380962

Version: 3.0

- 14. Has known allergies, hypersensitivity, or intolerance to mAbs, human proteins, or other product excipients.
- 15. Is a female who is pregnant, breastfeeding, or planning to become pregnant during GEN3017 treatment and within 4 months after the last dose of GEN3017.
- 16. Is a male who plans to father a child during GEN3017 treatment and within 4 months after the last dose of GEN3017.
- 17. Has any other serious, life-threatening or unstable pre-existing medical conditions, or uncontrolled intercurrent illness, including but not limited to active infection including COVID-19 infection.
- 18. Has any condition for which, in the opinion of the investigator, participation would not be in the best interest of the subject (eg, compromise the well-being) or that could prevent, limit, or confound the protocol-specified assessments. Additionally, vulnerable subjects or subjects under guardianship, curatorship, judicial protection or deprived of liberty), are excluded from participation in this trial.

5.3 Screen Failures

Screen failures are defined as subjects who consent to participate in the clinical trial but do not meet the protocol-defined eligibility criteria (refer to Sections 5.1 and 5.2) as assessed during screening. A minimal set of screen failure information is required to ensure transparent reporting of screen failure subjects to follow ICH guidelines, meet the CONSORT publishing requirements, and to respond to queries from regulatory authorities. Minimal information to be documented includes demography, reason for screening failure (eg, eligibility criteria not met, subject withdrew consent, or other reasons), and any AEs related to a protocol-mandated procedure (eg, CT scan), including washout or discontinuation of prior medications.

Individuals who do not meet the criteria for participation in this trial (ie, screen failures) may be rescreened one time. The rescreening must be approved by the sponsor to ensure that the safety of the subject is not compromised. All eligibility criteria must be reassessed at the rescreening visit. Previous baseline assessments (eg, imaging scans, certain labs) may be used for rescreening purposes if they are considered within the protocol required screening window for the newly planned C1D1 date. If updates have been made to the ICF since the subject's last

Confidential Page 64 of 162

Document Name: GCT3017-01 - Protocol - 18 Oct 2023 Genmab

Document Number: TMF-380962

Version: 3.0

signed ICF, rescreened subjects are required to sign a new ICF before rescreening procedures can be initiated.

Confidential Page 65 of 162

Version: 3.0

6 TRIAL TREATMENT

6.1 Investigational and Auxiliary Medicinal Products

Trial treatment is defined as any IMP, auxiliary medicinal product (AMP), or medical device(s) intended to be administered to a trial subject according to the trial protocol. IMP(s) specifically are referred to as trial drug(s).

Genmab

Trial treatment should be administered as described in Table 6-1 and Table 6-2 until 1 or more of the discontinuation criteria in Section 7 are met.

Detailed dose modification guidance is provided in Section 6.7. Information regarding concomitant therapy is provided in Section 6.6.

Table 6-1 Investigational Medicinal Product

Trial Drug Name	GEN3017 (DuoBody® CD3xCD30)a,b
Dosage Formulation	Concentrate for solution for CCI injection
Dose (including schedule and cycle length)	CCI
Route of Administration	CCI
Dosing Instructions	In expansion, 1) for adult subjects, GEN3017 will be administered as a injection with CC at the DL determined by the data from the dose escalation part. 2) For adolescent subjects with R/R cHL (US and Australia only; Cohort 2), GEN3017 will be administered as an CC Refer to Section 6.1.2 for premedication and post-GEN3017 treatment requirements. Refer to the IMP Manual for detailed instructions including drug dilution and injection volume.
Hospitalization/ Monitoring Guidance	During dose escalation in treatment Cycle 1, all subjects are required to be hospitalized for 24 hours after each GEN3017 administration. Subjects must be instructed to contact the investigator should signs or symptoms of CRS and/or ICANS occur following discharge from the hospital. During dose expansion in treatment Cycle 1, all subjects are required to remain at the clinic for monitoring CCI of GEN3017 for a minimum of 4 hours and hospitalization for 24 hours for CRS monitoring is required after CCI. Additional and prolonged hospitalization for monitoring subject's safety during GEN3017 administration CCI may be implemented per investigator's discretion. As data accumulate, increased (or reduced) monitoring may be implemented for additional dose administrations if recommended by the sponsor's Safety Committee.
Packaging	GEN3017 will be provided in 2R Glass Vials

Confidential Page 66 of 162

Document Name: GCT3017-01 - Protocol - 18 Oct 2023 Genmab

Document Number: TMF-380962

Version: 3.0

Labeling	Trial drug labels will contain information to meet the applicable regulatory requirements. For further details see the IMP Manual
----------	---

CD=cluster of differentiation; cHL=classical Hodgkin lymphoma; CRS=cytokine release syndrome; D=day; DL=dose level; EU=European Union; ICANS= immune effector cell-associated neurotoxicity syndrome; IMP=investigational medicinal product; CCl ; R/R=relapsed/refractory;

- a. Refer to the IMP Manual for further details.
- b. Refer to Section 10.18.1 for EU authorization status.

Confidential Page 67 of 162

Version: 3.0

 Table 6-2
 Auxiliary Medicinal Product(s)

AMP Name	Dexamethasone or methylprednisolone (or equivalent)	Paracetamol/ acetaminophen (or equivalent)	Diphenhydramine (or equivalent)	Tocilizumab	Siltuximab ^a	Anakinra ^a	
Use	CRS Premedication; CRS/ICANS management	CRS Premedication	CRS Premedication	CRS	CRS	CRS/ICANS	
Dosage/ frequency	Premedication: dexamethasone 20 mg, or methylprednisolone 100 mg, or equivalent 30 minutes to 2 hours prior to administration of GEN3017. CRS/ICANS management: dexamethasone 10-20 mg every 6 hours, or methylprednisolone 1000 mg/day	650 to 1000 mg, or equivalent 30 minutes to 2 hours prior to administration of GEN3017	50 mg, or equivalent 30 minutes to 2 hours prior to administration of GEN3017	8 mg/kg over 1 hour. Repeat after at least 8 hours as needed. Maximum of 2 doses in a 24-hour period.	11 mg/kg	100 mg to 200 mg once a day	
Route of Administration	IV	PO	IV or PO	IV	IV	SC	
Dosing Instructions	See Section 6.1.2 and Table 6-3; See Section 10.13 and Section 10.14	See Section 6.1.2 and Table 6-3	See Section 6.1.2 and Table 6-3	See Section 10.13 and Section 10.14	See Section 10.13 and Section 10.14	See Section 10.13 and Section 10.14	
Packaging	N/A	N/A	N/A	Vials	N/A	N/A	
Labeling	AMP labels will contain information to meet the applicable regulatory requirements.						

a. Refer to Section 10.18.1 for EU authorization status. Refer to Section 10.18.2 for country-specific information.

Confidential Page 68 of 162

Version: 3.0

6.1.1 GEN3017 Dosing Schedule

6.1.2 Premedication and Post-GEN3017 Monitoring

The purpose of the prophylactic premedication is to mitigate risk and severity of CRS by GEN3017. It is mandatory to premedicate subjects with corticosteroids, antihistamines, and/or antipyretics 30 minutes to 2 hours prior to the administration of GEN3017. Corticosteroid administration for premedication should be administered via IV infusions (Table 6-3) with the recommended dose or equivalent (Section 10.9).

CRS and/or ICANS should be proactively identified and promptly treated to prevent irreversible effects for which careful monitoring and timely management should follow ASTCT guidelines (Lee et al., 2019); Section 10.13 and Section 10.14). Investigators and study personnel must instruct subjects to contact the site if they experience signs and symptoms of CRS or ICANS (eg, fever, chills, dizziness, lightheadedness, syncope, dyspnea, neurologic symptoms, or altered mental status) for guidance on whether the subject must visit the study site or an alternative healthcare facility with experience in treating CRS/ICANS for further assessment and/or management (see Section 10.13 for CRS and Section 10.14 for ICANS assessments). Immediate access to tocilizumab is mandated on site.

[figure not shown]

Confidential Page 69 of 162

Genmab

Document Number: TMF-380962

Version: 3.0

6.2 Product Complaints

A product complaint is defined as any suspicion of a product defect related to manufacturing, labeling, or packaging, ie, any dissatisfaction relative to the identity, quality, durability, or reliability of a product, including its labeling or package integrity. A complaint may have an impact on the safety and efficacy of the product. Timely, accurate, and complete reporting and analysis of complaint information from trials are crucial for the protection of subjects, investigators, and the sponsor, and are mandated by regulatory agencies worldwide. The sponsor has established procedures in conformity with regulatory requirements worldwide to ensure appropriate reporting of complaint information; all trials conducted by the sponsor or its affiliates will be conducted in accordance with those procedures.

Product complaints must be reported to the sponsor's quality assurance (QA) department by trial-site personnel, within 24 hours of awareness of the event. The IMP Manual contains contact information (email and telephone) for Genmab QA and instructions for reporting complaints.

In addition to reporting the complaint, if the product defect is combined with an AE or serious adverse event (SAE), the trial-site personnel must report the AE or SAE to the sponsor according

Confidential Page 70 of 162

Version: 3.0

to the AE and SAE reporting process and timelines (refer to Section 8.4). A sample of the

suspected product should be maintained for further investigation if requested by the sponsor.

Genmab

6.3 Preparation/Handling/Storage/Accountability

6.3.1 Preparation, Handling, and Storage

Guidance for the preparation, handling, and storage of trial drug(s) is described in the IMP Manual.

6.3.2 Drug Accountability and Destruction

The investigator or designee must maintain an accurate record of received, returned, and/or destroyed IMP and administration of trial treatment to trial subjects in a drug accountability log/record. Drug accountability will be verified by the site monitor on a continuous basis and at the completion of the trial.

When drug accountability has been verified by the site monitor, all expired/unused trial IMP (eg, vials, capsules, prefilled syringes) can be destroyed or returned to the sponsor in accordance with the guidance in the IMP Manual.

Final drug accountability will be assessed at the end of the trial (or at site closure, if applicable) in accordance with local regulations and guidelines.

6.4 Measures to Minimize Bias: Randomization and Blinding

6.4.1 Treatment Assignment

This is an open-label trial; therefore, blinding of treatment will not be performed. Randomization will not be used in the dose escalation part of this trial.

During dose escalation, once a specific DL is open for enrollment, subjects will be assigned to that DL using an interactive response technology (IRT) system. Site personnel must contact the contract research organization (CRO) and the sponsor when a potential subject has been identified. If there is an open slot for enrollment, the site will be given approval to start the consenting and screening process. If there is no open slot, investigators should decide on the appropriate treatment for the subject should the subject require immediate anticancer treatment; otherwise, the subject may be placed on the waiting list, and the site will be alerted once an opening has become available.

During expansion, subjects will be allocated to individual disease cohorts (see Section 5.1.2) using an IRT system.

6.5 Compliance

The trial drug(s) will be administered in the controlled environment of a clinical research center, and the direct observation of trial drug(s) administration by trial staff will ensure compliance with trial requirements. The date and time of each trial treatment drug will be documented.

Treatment start and stop dates, including dates for trial drug(s) delays will also be documented.

Confidential Page 71 of 162

Document Number: TMF-380962

Version: 3.0

6.6 Prior and Concomitant Therapies

The sponsor's medical officer (or delegate) should be contacted if there are any questions regarding prior or concomitant medication or therapies.

6.6.1 Prior Anticancer Therapies

Prior anticancer therapies received from the time of initial diagnosis and until signing of informed consent for the treatment of study disease (including chemotherapy, radiotherapy, antibody-drug conjugates, immune CPIs, antibodies, transplantation, surgery, any investigational anticancer drugs etc) must be documented.

Genmab

The best response, reason for discontinuation, dates of administration, and date of progression should be reported for prior anticancer therapies.

Refer to Section 5.2 for details regarding prohibited prior anticancer therapies or washout periods for prior anticancer therapies.

6.6.2 Prior Therapies

Any medication, (including over-the-counter or prescription medicines, vitamins, and/or herbal supplements), vaccine, or blood transfusions received within 28 days before administration of the first dose of trial drug must be documented. Any SARS-COV-2 vaccines and seasonal flu vaccinations received within 3 months prior to the first dose of GEN3017 must be documented.

Refer to Section 5.2 for details regarding prohibited prior therapies or washout periods for prior therapies.

6.6.3 Concomitant Therapies

Subjects must be told to notify the trial site about any new medications (including over-the-counter or prescription medicines, vitamins, and vaccines) they take after the start of GEN3017. All medications (other than GEN3017) and significant nondrug therapies (including physical therapy, herbal/natural medications, and blood transfusions) administered during the trial (ie, beginning with administration of the first dose of GEN3017 until 30 days after the last dose of GEN3017) must be documented.

Investigators may prescribe concomitant medications or treatments deemed necessary to provide adequate supportive care except for those medications identified as "prohibited" (Section 6.6.3.2).

Concomitant therapies should also be documented beyond 30 days after the last dose of GEN3017 only in conjunction with worsening AEs or new SAEs related to GEN3017.

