6.6.3.2 Prohibited Concomitant Therapy

The sponsor must be notified in advance (or as soon as possible thereafter) of any instances in which prohibited therapies are administered.

The following concomitant therapies are prohibited from C1D1 until 30 days after last dose of GEN3017 unless otherwise specified:

Confidential Page 73 of 162

Version: 3.0

1. Any anticancer therapy intended for the treatment of lymphomas, eg, cytotoxic chemotherapy, immunotherapy, radiotherapy or experimental therapy.

Note: Radiation therapy is prohibited during the first treatment cycle. After the first cycle, radiation is permitted for palliative use only if documented radiographic disease progression is ruled out first.

- 2. Corticosteroid that exceeds a total daily dose of 25 mg of prednisolone or equivalent administered for more than 14 days unless for the management of AEs (excluding corticosteroids given as GEN3017 pre-infusion medication as prophylaxis as described in Section 6.1.2).
- 3. Live vaccines received within 30 days of the first dose of GEN3017, at any time during GEN3017 treatment, and for 3 months following the last dose of GEN3017.

Note: Seasonal influenza vaccines are generally killed virus vaccines and are permitted; however, intranasal influenza vaccines are live attenuated and are not allowed.

- 4. In the dose escalation part, administration of SARS-CoV-2 vaccine during the screening period and DLT period is not permitted.
- 5. Participation in any other investigational or interventional studies is not permitted.

Subjects who require the use of any of these agents will be discontinued from GEN3017 treatment. The sponsor must be notified. Subjects who are discontinued from GEN3017 treatment will be followed for safety outcomes for 60 days following the last dose of GEN3017 or until the subject receives a new anticancer therapy, whichever occurs first.

The above lists of medications are not necessarily all-inclusive. The investigator should contact the sponsor's MM if questions arise regarding medications not listed above.

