7.1.2 Safety Follow-up Visit(s)

Subjects discontinuing from treatment for any reason will have a safety follow-up visit 60 days (+14 days) after the subject receives the last dose of GEN3017. If the subject initiates new anticancer treatment within 60 days of the last dose of GEN3017, the safety follow-up visit should be performed prior to the initiation of the new anticancer treatment.

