8.4.2 Adverse Event Reporting

Trial Period	Reporting Requirements
Signing of ICF through prior to first dose	AEs, if assessed by the investigator to be caused by a protocol-mandated procedure (eg, CT scan), including washout or discontinuation of prior medications.
First dose through safety follow-up visit	All AEs and SAEs (see definitions in Section 10.2), regardless of casualty, will be documented.

Confidential Page 93 of 162

Document Number: TMF-380962

Version: 3.0

Safety follow-up visit through end of trial/after end of trial	There is no requirement to monitor subjects for SAEs following the protocol-required reporting period (ie, after the safety follow-up visit) or after end of trial. However, if the investigator becomes aware of an event, SAEs should be
	reported if judged by the investigator as related to trial drug(s).

NOTE: Any secondary primary malignancy(ies) (not a new lesion, recurrence, or transformation to a more aggressive histology of the disease under trial)] regardless of relatedness to trial drug(s), should be reported at any time during or after the trial if the investigator becomes aware of such an event.

For details regarding follow-up of AEs and SAEs, see Section 8.4.6. Refer to Section 6.2 for guidance regarding product complaints.

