9.3.4 Safety Analyses

Safety analysis will be done for both escalation and expansion part of the trial. The Safety Set will be used.

Adverse Events

The on-treatment period is defined as the time from C1D1 until the end of safety follow-up.

TEAEs are events that occur during the on-treatment period or AEs starting before C1D1 and worsening during the on-treatment period.

Adverse events will be graded according to the NCI-CTCAE as described in Section 10.2.3.1.

All TEAEs and treatment-emergent SAEs will be presented descriptively.

Analysis of AEs will be summarized using the Safety Set with the exception of deaths, which will be presented for the FAS.

Clinical Laboratory Tests

Grading of laboratory values will be assigned programmatically according to the NCI-CTCAE v5.0. The calculation of NCI-CTCAE grades will be based on the observed laboratory values only, clinical assessment will not be considered. CTCAE grade 0 will be assigned for all non-missing values not graded 1 or higher.

Laboratory tests that are graded by NCI-CTCAE are presented in a shift table presenting baseline grade versus worst on-treatment grade.

Laboratory tests that cannot be graded by NCI-CTCAE are presented in a shift table presenting baseline low/normal/high classification versus worst on-treatment value.

The number of subjects with at least 1 grade 3 or higher on-treatment laboratory test will be summarized.

Confidential Page 104 of 162

Version: 3.0

ICE Score

ICE score will be presented descriptively.

Constitutional Symptoms

Document Number: TMF-380962

Constitutional symptoms will be presented descriptively.

ECOG

ECOG will be presented descriptively.

ECG

Evaluation of ECG by investigator will be presented as normal/abnormal and not clinically significant/abnormal clinically significant.

ECG measurements (ie, QTc) will be presented by visit and time point. Abnormal values as read by central reader will be presented.

Vital Signs

Number of patients with at least 1 clinically notable abnormal value will be presented.

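### Routine recording of concomitant therapy stops 30 days after the last dose, but adverse events count as treatment-emergent to the 60-day safety visit, so some late events carry no required record of newly given therapy

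*Combined protocol and SAP*

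**What the plan says.** **Recording of therapy (6.6.3).** All medications other than GEN3017, and significant non-drug therapies including transfusions, are recorded from the first dose "until 30 days after the last dose of GEN3017) must be documented". Beyond that point, recording is required "only in conjunction with worsening AEs or new SAEs related to GEN3017".

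**Collection of adverse events (8.4.2).** From the first dose through the safety follow-up visit: "All AEs and SAEs (see definitions in Section 10.2), regardless of casualty, will be documented" (causality is evidently meant).

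**Timing of the visit (7.1.2).** Subjects who stop treatment "will have a safety follow-up visit 60 days (+14 days) after the subject receives the last dose of GEN3017". If new anticancer treatment starts within 60 days, "the safety follow-up visit should be performed prior to the initiation of the new anticancer treatment".

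**Analysis window (9.3.4).** "The on-treatment period is defined as the time from C1D1 until the end of safety follow-up", and "TEAEs are events that occur during the on-treatment period", together with earlier events that worsen in that period.

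**Prohibited therapy (6.6.3.2).** The listed therapies are "prohibited from C1D1 until 30 days after last dose of GEN3017 unless otherwise specified". One item, live vaccines, runs to 3 months after the last dose. The same section gives 60 days for safety follow-up.

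**The concern.** The period over which events are collected and tabulated is longer than the period over which the therapy around them must be recorded. Three things depend on that therapy record.

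- **Attribution.** For a new serious event after day 30, recording of other drugs is required only if the event is judged related to GEN3017. The causality judgment thus decides whether the data needed to review it are collected. Section 10.2.3.2 reports the last judgment when it changes, so an event first called unrelated may be reconsidered without a required medication record.
- **Recognising and reading laboratory events.** Under 10.2.2, the need for concomitant therapy is one of the things that makes a laboratory abnormality an adverse event. Section 9.3.4 grades laboratory values from the observed result alone and reports the worst on-treatment grade, while 6.6.3.1 permits transfusions and growth factors, which change those values.
- **Late events that resemble dose-limiting toxicities.** Section 6.7.2.1 takes events after the evaluation period that would have met the criteria into account for the recommended dose and the maximum tolerated dose. One criterion in 6.7.1 is grade 3 or higher thrombocytopenia that needs a platelet transfusion. A new, non-serious case more than 30 days after the last dose, if counted here, would turn on a transfusion whose recording is not required.

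**Working it through.** No power, alpha or sample-size figure is involved. The check compares two windows and then sorts events by what the text requires.

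**Inputs**
- End of routine recording: day 30 after the last dose (6.6.3).
- End of safety follow-up, F: day 60 nominal, day 74 at the latest, since 60 + 14 = 74; earlier if new anticancer treatment starts (7.1.2).
- End of the treatment-emergent window: the same F (9.3.4).

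**Formula.** Days without routine recording = max(0, F - 30). Share of the post-treatment window = that number divided by F.

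| F (days after last dose) | Days without routine recording | Share |
|---|---|---|
| 30 or less | 0 | 0% |
| 45 (illustration only) | 45 - 30 = 15 | 15/45 = 33% |
| 60 (nominal visit) | 60 - 30 = 30 | 30/60 = 50% |
| 74 (latest visit) | 74 - 30 = 44 | 44/74 = 59% |

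**Which events fall in the gap.** For events between day 31 and F, setting 6.6.3 beside 8.4.2 and 9.3.4 gives:

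| Event | Counts as treatment-emergent | Record of therapy newly given after day 30 required |
|---|---|---|
| New serious event, related | yes | yes |
| Worsening event, related | yes | yes |
| Worsening event, unrelated | yes | unclear |
| New serious event, unrelated | yes | no |
| New non-serious event, related or not | yes | no |

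The unclear row arises because the exception can be read two ways: the relatedness condition may apply to serious events only, or to worsening events as well. Therapy not linked to any event, such as background medication newly started after day 30, also has no required record.

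**How many subjects.** The planned total is about 120 + 120 = 240. That is a ceiling on subjects who could be affected, not an estimate. The documents do not say how many are expected to remain in safety follow-up beyond day 30.

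**The case against.** The strongest reply is that the 30-day limit is explicit, carries its own exception and matches the 30-day window in 6.6.3.2, so it may be deliberate. That is possible. The text gives no reason for the difference from the 60-day event window, however, and the exception leaves the last two rows of the table above uncovered. The amendment summary records a change of safety follow-up from 30 to 60 days, and a reader might infer that the 30 in 6.6.3 was left behind. That is conjecture. The point rests on the current text alone.

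Several stronger readings are tempting but not supported:

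- **That the second half of follow-up has no treatment data.** Therapy given up to day 30 is recorded, so a drug started by then and preceding a late event is known. The exception cases are recorded. Subjects must tell the site about new medications, with no stated end date (6.6.3). Site source records list concomitant medications without a day limit (10.1.11.1), and procedures are documented separately (8.1.4). What is missing is a requirement for routine recording of newly given therapy after day 30.
- **That attribution can never be re-checked.** Serious events are reported within 24 hours without a causality filter (8.4.3.2) and, if ongoing at the safety visit, are followed until resolved or chronic (8.4.6). Source documents are kept for 25 years (10.1.10.2). Review is harder, not impossible.
- **That an adjusted analysis fails.** The trial is exploratory (9.1) and treatment-emergent events are only described (9.3.4).
- **That every subject has the full gap.** Those who die or start new anticancer treatment by day 30 have none; those who start between days 31 and 60 have less than 30 days.
- **That late events of special interest are a large part of it.** Clinical tumor lysis syndrome requires laboratory changes within 7 days after the start of therapy (10.16), so it would hardly arise here.

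One thing cannot be settled: the Schedule of Activities is redacted, so any medication review listed there for the safety visit cannot be seen.

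**Conclusion.** The mismatch stands, as a minor point. No readable section aligns the 30-day recording limit with the 60 (+14) day event window. For up to 30 days (44 at the latest visit), in subjects still in safety follow-up after day 30, new non-serious events and serious events judged unrelated are tabulated as treatment-emergent without a required record of therapy newly given after day 30. The harm is to attribution and interpretation of late events. It does not reach the expansion response rate or the count of dose-limiting toxicities in the Cycle 1 window.

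This rests on two assumptions: that the redacted Schedule of Activities does not already require medication recording to the safety visit, and that source records listing medications are not equivalent to required documentation for the trial database. If the first is wrong, only the wording of 6.6.3 needs correcting.

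**What to change.** In 6.6.3, extend routine documentation of concomitant therapy so that it ends at the safety follow-up visit or at the start of new anticancer therapy, whichever comes first. Revise the sentence on recording beyond 30 days so that it begins where the new window ends, and make clear whether the relatedness condition applies to worsening events as well as to new serious events. Carry the change into the CRF guidance.

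The sponsor should also confirm whether the separate 30-day window for prohibited therapy in 6.6.3.2 is intended alongside the 60-day safety follow-up. That is a question about consistency; no clinical rule is proposed here.

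The cost is one changed window, one revised sentence, and up to about 30 more days of medication log per subject (44 at the latest visit), closed at a visit that is already scheduled. If the sponsor prefers to keep the 30-day limit, 6.6.3 should give the reason, and 9.3.4 should note that events after day 30 may lack concomitant-therapy data.
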